10.1.1 QT PROLONGATION

QTc interval has been observed in dogs at relatively low doses of enasidenib. Prolonged QTc interval has not been seen in other animal species at high doses. Subjects who experience prolongation of the heart-rate corrected QT interval, Fridericia's correction (QTcF) to > 480 msec (Grade ≥ 2) while treated with enasidenib, should be promptly evaluated for causality of the QTc prolongation and managed according to the following guidelines:

- Levels of electrolytes (potassium, calcium, and magnesium) should be checked and supplementation given to correct any values outside the normal range.
- Concomitant medications should be reviewed and adjusted as appropriate for medication with known QT prolonging effects.

in Patients with Accelerated/Blast-phase Myeloproliferative Neoplasm or Chronicphase Myelofibrosis with an IDH2 Mutation

(Myeloproliferative Neoplasms Research Consortium [MPN-RC] 119)

- If no other cause is identified and the Investigator believes it is appropriate, particularly if QTc remains elevated (after above measures have been implemented, or as determined by the Investigator), investigational product may be interrupted, and an ECG should be rechecked in approximately 1 week after the QTc prolongation was first observed, or more frequently as clinically indicated.
 - o If QTc has recovered or improved and the Investigator believes it is safe to do so, re-challenge with enasidenib should be considered if held. ECGs should be conducted at least weekly (e.g., at every scheduled visit) for 2 weeks following QTc reduction ≤ 480 msec.
 - If Grade 2 (QTcF> 480 and ≤ 500 msec), the dose of enasidenib may be reduced to a dose approved by the Study Chair without interruption of dosing. The enasidenib dose may be re-escalated to the prior dose in ≥ 14 days after QT prolongation has decreased to ≤ Grade 1.
 - If Grade 3 (QTcF> 500 msec), when QTc prolongation is first observed, hospitalization for continuous cardiac monitoring and evaluation by a cardiologist should both be considered. Dosing with enasidenib will be interrupted. If QTc returns to within 30 ms of baseline or < 450 msec within 14 days, treatment may be resumed at a reduced dose. The enasidenib dose cannot be re-escalated following dose reduction for Grade 3 QTcF prolongation unless the prolongation was associated with an electrolyte abnormality or concomitant medication.
 - If Grade 4 (QTcF> 500 msec or > 60 msec change from baseline with torsade de pointes or polymorphic ventricular tachycardia or signs/symptoms of serious arrhythmia), subjects should be admitted to hospital when QTc prolongation is first observed for continuous cardiac monitoring and be discharged only after review by a cardiologist. Dosing with enasidenib should be permanently discontinued.

10.1.2ABNORMAL LEVEL OF LIVER ENZYMES(HYPERBILIRUBINEMIA)

Subjects with elevations in $ALT \ge 3$ -fold ULN, subjects will be monitored using the algorithm:

- Repeat LFT (i.e., ALT, AST, total bilirubin, ALP, GGT) within < 3 days of the initial test. Follow-up 2-3 times weekly, and weekly when stable.
- Perform additional diagnostic follow up:
 - Focused medical history, including review of prior history of liver or biliary disorders, concurrent symptoms, review of all concomitant medications (e.g., acetaminophen-containing medications, over-the-counter or herbal medications, nutritional supplements) including any changes in medications, detailed review of alcohol use.
 - Hepatitis serology (anti-HAV, HBsAg, anti-HBs, anti-HB core, anti-HCV, HCV RNA, EBV and CMV screen), and autoantibodies (e.g., ANA, anti-smooth muscle antibody).
 - Complete physical examination.
 - Liver ultrasound and follow-up imaging as appropriate.
 - Additional evaluation as appropriate (INR, PT).

Hyperbilirubinemia generally decreased in frequency as enasidenib treatment continued. $\$

in Patients with Accelerated/Blast-phase Myeloproliferative Neoplasm or Chronicphase Myelofibrosis with an IDH2 Mutation

(Myeloproliferative Neoplasms Research Consortium [MPN-RC] 119)

 Table 1. Ruxolitinib initial dose for patients' baseline platelet count by cohort*

Cohort	Plt>100 X10 ⁹ /L	Plt 50-100 X10 ⁹ /L	Plt 20-50 X10 ⁹ /L	Plt<20 X10 ⁹ /L
Blast/Accelerated Phase	20 BID	15 BID	10 BID	5 BID
Chronic Phase	15 BID	10 BID**	NA	NA

*Patients already receiving Ruxolitinib will begin trial at the dose they were on prior to combination therapy. **Chronic phase patients with platelet<75 will not be enrolled to the trial.

Table 2a. Ruxolitinib Dose Adjustment for patients with accelerated and blast phase MF for NON-HEMATOLOGICAL AEs*

Dose level	PATIENTS' BASELINE PLATELET COUNTS			
	Plt>100 X10 ⁹ /L	Plt 50-100 X10 ⁹ /L	Plt 20-50 X10 ⁹ /L	Plt<20 X10 ⁹ /L
+1	25 BID	20 BID	NA	NA
0	20 BID	15 BID	10 BID	5 BID
-1	15 BID	10 BID	5 BID	5QD
-2	10 BID	5 BID	5 QD	Stop treatment
-3	5 BID	5 QD	Stop treatment	
-4	5 QD	Stop treatment		
-5	Stop treatment			

* For patients with accelerated and blast phase MF, treatment will continue at the same dose regardless of platelet count.

Table 2b. Ruxolitinib Dose Adjustment for patients with chronic phase MF for thrombocytopenia or nonhematological AEs

Dos	e level	DOSE ADJUSTMENT FOR THROMBOCYTOPENIA		
		Plt>100 X10 ⁹ /L	Plt 50-100 X10 ⁹ /L	Plt 20-50 X10 ⁹ /L
	+1	20 BID	15 BID	N/A
DOSE ADJUSTMENT FOR NON- HEMATOLOGICAL AES	15 BID	10 BID	5 BID*	
	-1	10 BID	5 BID	5 QD
	-2	5 BID	5 QD	Stop treatment
	-3	5 QD	Stop treatment	
	-4	Stop treatment		

MPN-RC

A Phase II Open-label Study of Combined Ruxolitinib and Enasidenib Sinai in Patients with Accelerated/Blast-phase Myeloproliferative Neoplasm or Chronic-

phase Myelofibrosis with an IDH2 Mutation

(Myeloproliferative Neoplasms Research Consortium [MPN-RC] 119)

 Table 3a. Enasidenib Dose Adjustment for thrombocytopenia

MF chronic phase Cycle 1	MF chronic phase Cycle 2 and above	MF chronic phase Cycle 2 and above	MF chronic phase Cycle 2 and above	MF accelerated phase and blast phase
Platelet >75X10 ⁹ /L	Platelet > 50X10 ⁹ /L	Platelet 35-50X10 ⁹ /L	Platelet<35X10 ⁹ /L	Any platelet count
50mg	100mg	50mg	Hold	100mg

Table 3b. Enasidenib Dose Adjustment for non-hematological AE

Dose Level	Enasidenib
-1	50 mg QD
0	100 mg QD

MPN-RC

10.2 DOSE MODIFICATIONS FOR HEMATOLOGICAL AE'S

For subjects receiving ruxolitinib and enasidenib, ruxolitinib dosages will be adjusted as detailed in **Table 2a** and **Table 2b**.

For chronic phase MF, if platelets are reduced to $< 20X10^{9}/L$ ruxolitinib should be stopped

Ruxolitinib can be rechallenged at 5mg BID when platelets recover to $>20X10^{9}/L$, and enasidenib could be added the subsequent cycle as long as platelets recover to $>50X10^{9}/L$.

Interrupt treatment for absolute neutrophil count (ANC) less than 0.5 X 10^9 /L. After recovery of ANC above 0.75 X 10^9 /L, dosing may be restarted; restart dosing at 5 mg per day lower than the dose prior to the treatment interruption.

For patients with accelerated and blast phase MF, treatment will continue at the same dose regardless of platelet count or ANC.

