10. TREATMENT DOSAGE AND ADMINISTRATION

Patients who are on ruxolitinib will continue their current dose. Patients who are not on ruxolitinib will receive ruxolitinib per Table 1 dosing based on platelet count (modified package insert dosing). Enasidenib will be given at 100 mg daily on enrollment for patients with accelerated and blast phase myelofibrosis regardless of platelet count (this will be deemed Cycle 1). Patients with chronic phase myelofibrosis will receive Enasidenib at starting dose of 50 mg daily for cycle 1. The dose of Enasidenib will be increased to 100 mg for cycle 2 if the platelet count stays above 50,000 at the end of cycle 1 (Table 3a) and no other therapy emergent SAE of grade \geq 2 developed (except grade 2 hyperbilirubinemia that is acceptable for dose escalation).

Ruxolitinib and enasidenib will be given orally in an outpatient setting unless the patient is being seen inpatient for another reason. Ruxolitinib and enasidenib will be given orally in 28-day cycles.

Patients should fast 2 hours before and 1-hour post enasidenib. Ruxolitinib may be administered independent of fasting and may be given with enasidenib. All protocol mandated visits will be performed at one of the participating institutions. Patients will return to the treating institution at a minimum of weekly during Cycles 1 and 2, every 4 weeks for Cycles 3 and beyond. Additional clinic visits will be mandated according to the patient clinical condition and at the discretion of the treating provider. Patients will have an end of study visit for a safety follow-up at 30 days after their last dose of therapy.

The dosages of ruxolitinib and/or enasidenib can be reduced, based on assessment of adverse events, if any occur, as described below in Section 10.1. Missed or vomited doses of ruxolitinib or enasidenib will not be made up.

Twenty-eight days is considered one cycle of therapy. Attempts will be made to provide an adequate treatment period with the combination of at least 6 cycles, unless significant toxicity is observed, to account for delayed time to response observed with biologic agents. Responders will continue therapy indefinitely unless progression of disease occurs, toxicity warranting discontinuation of therapy is

A Phase II Open-label Study of Combined Ruxolitinib and Enasidenib Sinai in Patients with Accelerated/Blast-phase Myeloproliferative Neoplasm or Chronic-

phase Myelofibrosis with an IDH2 Mutation

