If drug-related Grade 3 clinically relevant non-hematologic toxicity is attributable to one or both of the drugs (based on known adverse events profile), dose interruption of that particular drug(s) is mandatory. Patients who experience Grade 3 drug related clinically relevant non-hematological toxicity may be given a subsequent course one dose level below the previous course, but the patient must have recovered to Grade ≤ 1 before initiation of the next course. If attributable to ruxolitinib, dosing modifications in Tables 2a and 2b should be utilized. If attributable to enasidenib, dosing modification in Table 3b should be utilized. If a patient has drug-related clinically relevant Grade 4 non-hematologic toxicity, he/she will be taken off study. The dose of therapeutic agents can be decreased, at the discretion of treating physician, for chronic Grade 2 non-hematologic toxicity. Additionally, ruxolitinib dosage may be adjusted if patients develop decline in Creatinine clearance (CrCl) as calculated by the Cockcroft- Gault equation as follows: Reduce ruxolitinib dose by one dose level for patients with moderate (CrCl 30-59 mL/min) or severe renal impairment (CrCl 15-29 mL/min) if the patient is receiving a ruxolitinib dose of 10 mg BID or higher. (Per FDA package insert for ruxolitinib).

Myelosuppression and cytopenias are expected outcomes of MF disease processes and MF treatments and per se will not constitute adverse events except as follows: hematologic toxicity will be considered Grade 4 neutropenia with fever that does not clinically resolve within 14 days in the setting of optimal interventions or Grade 4 thrombocytopenia with clinically-significant bleeding. Dose interruption of the drug to which the adverse event is attributable is required. Patients may be given a subsequent course one dose level below the previous course, but the patient must have recovered to grade \leq baseline at study entry. The dose of therapeutic agents can be decreased, at the discretion of treating physician, for chronic Grade 3 hematologic toxicity.

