10.3 DOSE ESCALATIONS

Patients may be escalated to the next higher dose level of ruxolitinib as per dose levels in Table 2a in the event that a patient's platelet count increases, after Cycle 3 of combined therapy or in case of suboptimal response in the opinion if the investigator. Patients with chronic phase MF will escalate the dose of enasidenib from 50mg to 100 mg in cycle 2 and ongoing if platelet count stays above 50,000 at the end of cycle 1 (Table 3a) and no other therapy emergent SAE of grade \geq 2 developed (except grade 2 hyperbilirubinemia that is permitted).

Dose of ruxolitinib and enasidenib cannot be simultaneously increased in the same cycle. Dose escalation is permitted if *ALL* of the following criteria are met:

- 1. No dose reductions due to toxicity were required in the prior cycle
- 2. No dose interruptions due to toxicity were required in the prior cycle
- 3. The prior cycle was not delayed due to toxicity
- 4. The current cycle is not delayed due to toxicity

A Phase II Open-label Study of Combined Ruxolitinib and Enasidenib Sinai in Patients with Accelerated/Blast-phase Myeloproliferative Neoplasm or Chronic-

phase Myelofibrosis with an IDH2 Mutation

(Myeloproliferative Neoplasms Research Consortium [MPN-RC] 119)

5. ANC $\geq 1.0 \times 10^{9}/L$

MPN-RC

- 6. The patient has sub-optimal benefit, defined as a failure to reduce palpable spleen length by at least 50% and/or suboptimal improvement in disease- related symptoms as assessed by the Investigator.
- 7. No development of new on set transfusion dependency judged to be due to therapy

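### Section 10.2's fixed 5 mg BID ruxolitinib rechallenge has no cap, so a chronic-phase patient stopped on 5 mg QD may restart at twice that dose

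*Combined protocol and SAP*

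**What the plan says.** Section 10.2 sends ruxolitinib adjustments to Tables 2a and 2b, then adds rules for chronic phase. Ruxolitinib stops at platelets below 20 x 10^9/L. After that, "Ruxolitinib can be rechallenged at 5mg BID when platelets recover to" above 20. No other rechallenge dose is named, and the dose before the stop is not mentioned. The neutrophil rule in the same section works differently: it restarts 5 mg/day below the dose in use at the interruption.

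The chronic-phase table is headed "Table 2b. Ruxolitinib Dose Adjustment for patients with chronic phase MF for thrombocytopenia or nonhematological AEs". Its columns are platelet bands and its rows are dose levels. The lowest active dose is 5 mg QD. Patients already on the drug do not start from the table: "Patients who are on ruxolitinib will continue their current dose". No minimum is given.

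Section 10.3 sets conditions for dose escalation, among them "No dose interruptions due to toxicity were required in the prior cycle". For ruxolitinib it says "Patients may be escalated to the next higher dose level of ruxolitinib as per dose levels in Table 2a", which is the accelerated/blast-phase table.

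Section 10.1 says of cytopenias that they "per se will not constitute adverse events except as follows". For platelets, the exception is Grade 4 thrombocytopenia with clinically significant bleeding, and only then does its restart rule of one level lower apply.

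**The concern.** A restart after a platelet stop should not exceed the dose that preceded the fall. Sections 18.1.1 and 18.3 describe ruxolitinib's cytopenias as dose-related, and Section 10.1 notes that this combination has not been used before in this population. A fixed restart dose is safe only if nobody is below it at the stop, and the protocol lets chronic-phase patients be on half of it. The neutrophil rule in 10.2 and the bleeding rule in 10.1 both restart lower than before. The platelet rule is the only one of the three that can restart higher. What is at stake is a second severe platelet fall in an individual patient, not an operating characteristic of the trial.

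**Working it through.** No sample size, power or error rate is involved. The check is daily-dose arithmetic plus a cross-reading of the dosing rules.

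**Step 1. Restart dose relative to the dose at the stop.** Daily dose = tablet dose x doses per day. The restart is 5 x 2 = 10 mg/day.

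| Dose at stop | mg/day | Restart / dose at stop |
|---|---|---|
| 20 BID | 40 | 10/40 = 0.25 |
| 15 BID | 30 | 10/30 = 0.33 |
| 10 BID | 20 | 10/20 = 0.5 |
| 5 BID | 10 | 10/10 = 1.0 |
| 5 QD | 5 | 10/5 = 2.0 |

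Of these doses, only 5 mg QD leads to a higher restart.

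**Step 2. Who can be on 5 mg QD when platelets cross 20.** Table 2b, with the row above level -1 read as level 0 (its label is lost in the text):

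| Level | Plt >100 | Plt 50-100 | Plt 20-50 |
|---|---|---|---|
| 0 | 15 BID | 10 BID | 5 BID (starred) |
| -1 | 10 BID | 5 BID | 5 QD |
| -2 | 5 BID | 5 QD | Stop |
| -3 | 5 QD | Stop | (blank) |

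The routes are:

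- Level -1, for example after one non-hematological reduction, with platelets now at 20-50: the table dose is 5 QD.
- The neutrophil step-down from 5 BID: 10 - 5 = 5 mg/day.
- A carried-over entry dose of 5 QD, since no minimum is stated.
- 5 QD at level -2 (platelets 50-100) or level -3 (above 100), if platelets fall through the next band between visits. With a gradual fall, the table stops these patients before 20 is reached.

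**Step 3. Section 10.2 against Table 2b once platelets are back at 20-50.**

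- Level 0: both give 10 mg/day.
- Level -1: 10.2 allows 10 mg/day; the table gives 5 mg/day.
- Level -2: 10.2 allows 10 mg/day; the table gives 0.

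The two rules agree only for a patient reduced for platelets alone.

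**Step 4. Whether Section 10.3 closes the gap.** Its interruption criterion looks back to the prior cycle. Section 10 schedules visits "at a minimum of weekly during Cycles 1 and 2, every 4 weeks for Cycles 3 and beyond". In Cycles 1 and 2, a stop at Day 8 and a restart at Day 22 fall in one cycle, so the criterion is not triggered. From Cycle 3, a stop at one scheduled visit and a restart at the next puts the interruption in the prior cycle, and the criterion would bar an increase if it applies to rechallenge and if the interruption counts as toxicity. Section 16.8 suggests that it can count: a laboratory abnormality that leads to dose interruption is an adverse event there. Section 10.1 points the other way for cytopenias without bleeding. Section 10.3 does not mention the 10.2 rechallenge, and 10.2 does not refer to 10.3.

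**The case against.** The best defense is that 10.2 should be read as a whole. Its opening sentence makes Table 2b mandatory, while the rechallenge sentence is permissive. Since 5 BID is the level-0 dose at platelets 20-50, the sentence may only restate the base dose, with the table's reductions still in force. On that reading a patient reduced under Table 2b is not doubled. This is reasonable, but the text does not say it: the rechallenge sentence names one dose without reference to level. Nor would it help a patient who reached 5 QD by the neutrophil step or a carried-over entry dose, because neither is a table level.

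A second defense is the asterisk on 5 BID in Table 2b at platelets 20-50, whose footnote is not in the text available. It may have been lost in reading the PDF. If it caps the dose, the point falls. It cannot be presumed to do so.

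A third is that Section 10.3 already forbids the increase. That stands in part, mainly from Cycle 3 onward. Where it does hold, 10.3 forbids what 10.2 allows, and the text still needs reconciling.

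Two wider readings are tempting. One is that enasidenib has the same gap, because 10.2 gives a re-add threshold without a dose and "Table 3a. Enasidenib Dose Adjustment for thrombocytopenia" gives 100 mg above 50. The documents do not support it as a fault. That table titrates by platelets by design, the re-add comes in a later cycle where the interruption criterion may apply, and Section 18.2.1 does not list thrombocytopenia among enasidenib's hematologic effects. The other is that the problem is common because 5 QD appears in every column. As platelets fall through the bands, most of those cells lead to a stop.

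**Conclusion.** The point holds for ruxolitinib in chronic-phase patients on 5 mg QD at the stop. Section 10.2 permits a restart at 2.0 times the dose on which platelets fell below 20. At platelets 20-50 that is 10 versus 5 mg/day against Table 2b at level -1, and 10 versus 0 at level -2. From any higher dose in the table the restart is equal or lower.

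The reach is small. The chronic-phase cohort is descriptive and takes at most 10 patients (Sections 11.4 and 21), the sequence is uncommon, and the treating physician may choose a lower dose. The documents give no rate for it, so no expected number of patients is offered. The accelerated/blast-phase cohort keeps its dose regardless of platelets or neutrophils (Section 10.2), so the primary analysis is unaffected. The conclusion rests on the unseen Table 2b footnote not already capping the dose, and on reading the neutrophil rule, which names no drug, as applying to ruxolitinib.

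**What to change.** In Section 10.2, let ruxolitinib be rechallenged at 5 mg BID or at the dose in use at the stop, whichever is lower, with any later increase made under Section 10.3. First check the Table 2b footnote in the source document; if it already caps the dose, no change is needed. The cost is one clause. Under Section 25.4 it needs an amendment and IRB approval, and it can go with the next planned amendment. It adds no visits, tests or patients.

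### Sections 10.1 and 10.2 conflict on dosing after hematologic toxicity in accelerated/blast-phase patients, and 10.2 points to a table titled for non-hematological events

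*Combined protocol and SAP*

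**What the plan says.** **Section 10.1.** The heading is for non-hematological events, but the section also contains a paragraph on hematologic ones. Cytopenias are treated as expected and do not count as adverse events in themselves, with two exceptions. One is "Grade 4 thrombocytopenia with clinically-significant bleeding"; the other is given as "hematologic toxicity will be considered Grade 4 neutropenia with fever that does not clinically resolve within 14 days in the setting of optimal interventions". For these, "Dose interruption of the drug to which the adverse event is attributable is required". After recovery to the grade at study entry or better, "Patients may be given a subsequent course one dose level below the previous course". The paragraph ends: "The dose of therapeutic agents can be decreased, at the discretion of treating physician, for chronic Grade 3 hematologic toxicity". None of these sentences is restricted to chronic-phase patients.

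**Section 10.2.** The heading is for hematological events. The opening sentence says that for subjects on both drugs "ruxolitinib dosages will be adjusted as detailed in" Tables 2a and 2b. A later sentence interrupts treatment when the ANC falls below 0.5 × 10⁹/L and restarts it at a lower dose once the ANC is above 0.75 × 10⁹/L. It names no cohort. The last sentence says that for AP/BP patients "treatment will continue at the same dose regardless of platelet count or ANC".

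**Tables.** Table 2a is titled "Ruxolitinib Dose Adjustment for patients with accelerated and blast phase MF for NON-HEMATOLOGICAL AEs". Its footnote keeps AP/BP patients on the same dose whatever the platelet count and does not mention the ANC. Table 2b, for chronic phase, covers both thrombocytopenia and non-hematological events. Table 3a gives AP/BP patients enasidenib 100 mg at any platelet count. Table 3b holds the 50 mg level and is titled for non-hematological events.

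**Section 10.7.** It foresees ruxolitinib being held abruptly for events such as major bleeding or marked thrombocytopenia, in any patient.

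**The concern.** An AP/BP patient can satisfy a rule that requires interruption and a rule that requires treatment to continue unchanged, and the protocol does not say which takes precedence. AP/BP is the primary cohort, and severe cytopenia is plainly anticipated in it. The platelet minimum in the inclusion criteria applies to chronic phase only, and Table 1 gives a starting dose even for platelets below 20 × 10⁹/L.

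The first stake is safety, because two sites could handle the same event differently and each cite the protocol.

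The second is consistency of exposure behind the primary endpoint, which is response within 6 cycles. The choice of passage also carries forward. Under Section 10.3 a toxicity-related interruption or reduction in the prior cycle blocks dose escalation. Under Section 27 a toxicity that needs dose modification or suspension and does not recover to baseline ends treatment in a patient with less than a CRi.

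**Working it through.** The plan states no figure on this point, so the check sets the passages side by side for an AP/BP patient.

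| Situation | Section 10.1 | Section 10.2 | Tables |
|---|---|---|---|
| Grade 4 thrombocytopenia with significant bleeding | Interruption required; later course may be one level lower | Same dose whatever the platelet count | 2a footnote: same dose. 3a: 100 mg at any platelet count |
| Grade 4 neutropenia, fever unresolved at 14 days | Interruption required; later course may be one level lower | Last sentence: same dose whatever the ANC. Earlier sentence: interrupt below 0.5, cohort not named | 2a footnote silent on ANC |
| Chronic Grade 3 hematologic toxicity, no fever or bleeding | Reduction allowed at physician's discretion | Same dose | 2a and 3b titled for non-hematological events |
| ANC below 0.5 × 10⁹/L, uncomplicated | Not an adverse event in itself | Interrupt (no cohort named), then same dose for AP/BP | 2a footnote silent on ANC |

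Two readings could harmonise the text.

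1. *Section 10.2 covers counts alone and Section 10.1 covers complicated cytopenia.* This settles rows 1 and 2 in favour of interruption. It does not settle row 3, because the chronic Grade 3 sentence requires no clinical complication and names no phase.
2. *The AP/BP sentence in 10.2 is a cohort-specific exception to everything before it.* This would settle rows 3 and 4, but it settles rows 1 and 2 the opposite way from reading 1. It also sits badly with Section 10.7, which has no phase limit.

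The protocol states neither reading, and the two give opposite instructions for the same bleeding patient.

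Neither reading repairs the table reference. Section 10.2 sends hematologic adjustment to Table 2a, and the title of Table 2a excludes that use. The footnote does supply a rule for platelets, but not for the ANC that Section 10.2 adds. For enasidenib the only lower level outside the chronic-phase columns is in Table 3b, under a title with the same restriction.

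**Size.** The cohort has at most 20 evaluable patients (22 enrolled). Those affected are the AP/BP patients who have one of the events above, which could be anywhere from none to all of them. The background section reports febrile neutropenia as a serious event in 23.9% (79 of 330) in the earlier enasidenib study. That is a different event definition in a different population, so it is not used here as an estimate.

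**The case against.** The strongest reply is that Section 10.2 speaks only of counts. It does not tell a site to continue regardless of bleeding or unresolved fever. Section 10.1 itself draws the line between cytopenia as such and cytopenia with a complication. Section 10.7 expects ruxolitinib to be held for major bleeding. Section 27 stops treatment for events that the investigator judges may cause severe or permanent harm. On this view no site would dose through a major bleed. For the two Grade 4 events this is plausible, and it is why the point is a request for reconciliation. It remains an inference, though, and it does not reach the chronic Grade 3 sentence or the table reference.

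Three stronger claims might be inferred, and the documents do not support them.

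- *That AP/BP patients must have their dose reduced under Section 10.1.* Only interruption is mandatory; the lower level is permitted. Mandatory interruption is enough to conflict with continuing at the same dose.
- *That no dose levels exist for these patients.* Table 2a lists AP/BP ruxolitinib levels down to stopping, and Section 10.3 already uses it for escalation when the platelet count rises. The fault is that its title excludes the use to which Section 10.2 puts it.
- *That all AP/BP patients are affected.* Only those who have such an event are.

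**Conclusion.** The inconsistency stands. On the text, the same AP/BP patient with a Grade 4 event defined in Section 10.1 meets both a required interruption and a same-dose rule. A patient with chronic Grade 3 hematologic toxicity meets both a permitted reduction and a same-dose rule. The cohort for the ANC interruption in Section 10.2 is unclear until its last sentence is read as overriding it. The titles of Tables 2a and 3b do not match the hematologic use that Sections 10.1 and 10.2 require of them.

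The conclusion rests on the wording alone and assumes that no text outside the supplied documents sets an order of precedence. The number of patients affected cannot be derived from the documents, and no effect on the response rate is claimed. The design and its decision rule are untouched. The correction should still be made, because it is cheap and bears on safety in the primary cohort.

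**What to change.** Reconcile Sections 10.1, 10.2 and 10.7 with Tables 2a, 3a and 3b. For AP/BP patients the protocol should state:

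- which passage governs the two Grade 4 events defined in Section 10.1, and which governs chronic Grade 3 hematologic toxicity;
- whether the ANC interruption sentence in Section 10.2 applies to this cohort;
- which table supplies any dose levels, for ruxolitinib and for enasidenib.

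Then align the title and footnote of Table 2a with Section 10.2, including whether the footnote extends to the ANC, and make the title of Table 3b fit its intended use. Which clinical rule applies is for the sponsor to decide.

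The cost is a wording amendment, with no change to the sample size, the decision rule or the analyses.
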